#### 9.4 Comprehensive Adverse Events and Potential Risks List (CAEPR) for Atezolizumab (MPDL3280A, NSC 783608)

The Comprehensive Adverse Events and Potential Risks list (CAEPR) provides a single list of reported and/or potential adverse events (AE) associated with an agent using a uniform presentation of events by body system. In addition to the comprehensive list, a subset, the Specific Protocol Exceptions to Expedited Reporting (SPEER), appears in a separate column and is identified with bold and italicized text. This subset of AEs (SPEER) is a list of events that are protocol specific exceptions to expedited reporting to NCI (except as noted below). Refer to the 'CTEP, NCI Guidelines: Adverse Event Reporting Requirements' [http://ctep.cancer.gov/protocolDevelopment/electronic\\_applications/docs/aeguidelines.pdf](http://ctep.cancer.gov/protocolDevelopment/electronic_applications/docs/aeguidelines.pdf) for further clarification. *Frequency is provided based on 3097 patients.* Below is the CAEPR for Atezolizumab (MPDL3280A).

**NOTE:** PRO-CTCAE data should not be used for determining attribution, dose modifications, or reporting of serious adverse events.

**NOTE:** Report AEs on the SPEER ONLY IF they exceed the grade noted in parentheses next to the AE in the SPEER. If this CAEPR is part of a combination protocol using multiple investigational agents and has an AE listed on different SPEERs, use the lower of the grades to determine if expedited reporting is required.

Adverse Events with Possible Relationship to Atezolizumab (MPDL3280A) (CTCAE 5.0 Term) [n= 3097]			Specific Protocol Exceptions to Expedited Reporting (SPEER)
Likely (>20%)	Less Likely (<=20%)	Rare but Serious (<3%)	
BLOOD AND LYMPHATIC SYSTEM DISORDERS			
	Anemia		
CARDIAC DISORDERS			
		Heart failure 	
		Myocarditis 	
		Pericardial effusion 	
		Pericardial tamponade 	
		Pericarditis 	
ENDOCRINE DISORDERS			
		Adrenal insufficiency 	
		Endocrine disorders - Other (diabetes) 	
	Hyperthyroidism 		
		Hypophysitis 	
	Hypothyroidism 		
EYE DISORDERS			
		Eye disorders - Other (ocular inflammatory toxicity) 	
		Uveitis 	
GASTROINTESTINAL DISORDERS			
	Abdominal pain		Abdominal pain (Gr 2)
		Colitis 	
	Diarrhea		Diarrhea (Gr 2)
	Dysphagia		
	Nausea		Nausea (Gr 2)
		Pancreatitis 	
	Vomiting		Vomiting (Gr 2)
GENERAL DISORDERS AND ADMINISTRATION SITE CONDITIONS			
Fatigue			Fatigue (Gr 2)
	Fever 		
	Flu like symptoms 		
HEPATOBIILIARY DISORDERS			
		Hepatic failure 	
		Hepatobiliary disorders - Other [immune related (hepatitis)] 	
IMMUNE SYSTEM DISORDERS			
	Allergic reaction 		
		Anaphylaxis 	
		Cytokine release syndrome 	

Adverse Events with Possible Relationship to Atezolizumab (MPDL3280A) (CTCAE 5.0 Term) [n= 3097]			Specific Protocol Exceptions to Expedited Reporting (SPEER)
Likely (>20%)	Less Likely (<=20%)	Rare but Serious (<3%)	
		Immune system disorders - Other (hemophagocytic lymphohistiocytosis (HLH)/macrophage activation syndrome (MAS)) 	
		Immune system disorders - Other (systemic immune activation) 	
INFECTIONS AND INFESTATIONS			
Infection 			
INJURY, POISONING AND PROCEDURAL COMPLICATIONS			
	Infusion related reaction 		
INVESTIGATIONS			
	Alanine aminotransferase increased 		
	Alkaline phosphatase increased 		
	Aspartate aminotransferase increased 		
	Blood bilirubin increased 		
		Creatinine increased	
	GGT increased		
	Lipase increased*		
		Platelet count decreased	
	Serum amylase increased*		
METABOLISM AND NUTRITION DISORDERS			
	Anorexia		Anorexia (Gr 2)
		Hyperglycemia 	
	Hypokalemia		
	Hyponatremia		
MUSCULOSKELETAL AND CONNECTIVE TISSUE DISORDERS			
	Arthralgia 		
	Back pain		
		Generalized muscle weakness	
	Myalgia		
		Myositis 	
NERVOUS SYSTEM DISORDERS			
		Ataxia 	
		Encephalopathy 	
		Guillain-Barre syndrome 	
		Myasthenia gravis 	
		Nervous system disorders - Other (meningitis non-infective) 	
		Nervous system disorders - Other (facial paresis) 	

Adverse Events with Possible Relationship to Atezolizumab (MPDL3280A) (CTCAE 5.0 Term) [n= 3097]			Specific Protocol Exceptions to Expedited Reporting (SPEER)
Likely (>20%)	Less Likely (<=20%)	Rare but Serious (<3%)	
		Nervous system disorders - Other (encephalitis non-infective) 	
		Nervous system disorders - Other (immune-mediated myelitis) 	
		Paresthesia 	
		Peripheral motor neuropathy 	
		Peripheral sensory neuropathy 	
RENAL AND URINARY DISORDERS			
		Acute kidney injury	
		Renal and urinary disorders - Other (nephritis) 	
RESPIRATORY, THORACIC AND MEDIASTINAL DISORDERS			
	Cough		Cough (Gr 2)
	Dyspnea		
	Hypoxia		
	Nasal congestion		Nasal congestion (Gr 2)
		Pleural effusion 	
		Pneumonitis 	
SKIN AND SUBCUTANEOUS TISSUE DISORDERS			
		Bullous dermatitis 	
		Erythema multiforme 	
	Pruritus		
	Rash acneiform		
	Rash maculo-papular		
		Skin and subcutaneous tissue disorders - Other (drug reaction with eosinophilia and systemic symptoms [DRESS]) 	
	Skin and subcutaneous tissue disorders - Other (lichen planus) 		
		Skin and subcutaneous tissue disorders - Other (exanthematous pustulosis) 	
		Stevens-Johnson syndrome 	
		Toxic epidermal necrolysis 	

\*Denotes adverse events that are <3%.

This table will be updated as the toxicity profile of the agent is revised. Updates will be distributed to all Principal Investigators at the time of revision. The current version can be obtained by contacting [contact]. Your name, the name of the investigator, the protocol and the agent should be included in the e-mail.

Atezolizumab, being a member of a class of agents involved in the inhibition of “immune checkpoints,” may result in severe and possibly fatal immune-mediated adverse events probably due to T-cell activation and proliferation. Immune-mediated adverse reactions have been reported in patients receiving atezolizumab. Adverse events potentially related to atezolizumab may be manifestations of immune-mediated adverse events. In clinical trials, most immune-mediated adverse reactions were reversible and managed with interruptions of atezolizumab, administration of corticosteroids and supportive care.

Infusion reactions, including high-grade hypersensitivity reactions, anaphylaxis, and cytokine release syndrome, which have been observed following administration of atezolizumab, may manifest as fever, chills, shakes, itching, rash, hypertension or hypotension, or difficulty breathing during and immediately after administration of atezolizumab.

Infection includes all 75 sites of infection under the INFECTIONS AND INFESTATIONS SOC.

**Adverse events reported on atezolizumab (MPDL3280A) trials, but for which there is insufficient evidence to suggest that there was a reasonable possibility that atezolizumab (MPDL3280A) caused the adverse event:**

**BLOOD AND LYMPHATIC SYSTEM DISORDERS** - Blood and lymphatic system disorders - Other (pancytopenia); Febrile neutropenia

**CARDIAC DISORDERS** - Cardiac arrest; Ventricular tachycardia

**GASTROINTESTINAL DISORDERS** - Constipation; Dry mouth; Ileus

**GENERAL DISORDERS AND ADMINISTRATION SITE CONDITIONS** - Chills; Edema limbs; Malaise; Multi-organ failure

**HEPATOBIILIARY DISORDERS** - Portal vein thrombosis

**INVESTIGATIONS** - Lymphocyte count decreased; Neutrophil count decreased; Weight loss; White blood cell decreased

**METABOLISM AND NUTRITION DISORDERS** - Hypophosphatemia; Tumor lysis syndrome

**MUSCULOSKELETAL AND CONNECTIVE TISSUE DISORDERS** - Bone pain; Muscle cramp; Pain in extremity

**NERVOUS SYSTEM DISORDERS** - Headache

**PSYCHIATRIC DISORDERS** - Confusion; Insomnia; Suicide attempt

**REPRODUCTIVE SYSTEM AND BREAST DISORDERS** - Breast pain

**RESPIRATORY, THORACIC AND MEDIASTINAL DISORDERS** - Bronchopulmonary hemorrhage; Pulmonary hypertension; Respiratory failure

**SKIN AND SUBCUTANEOUS TISSUE DISORDERS** - Alopecia; Dry skin; Hyperhidrosis

**VASCULAR DISORDERS** - Hypertension; Hypotension; Thromboembolic event

**Note:** Atezolizumab (MPDL3280A) in combination with other agents could cause an exacerbation of any adverse event currently known to be caused by the other agent, or the combination may result in events never previously associated with either agent.

## 9.5 CDUS Monitoring

The assigned monitoring method for this protocol is CDUS-Abbreviated.

This study will be monitored by the Clinical Data Update System (CDUS) Version 3.0. Cumulative protocol- and patient-specific CDUS data will be submitted electronically to CTEP on a quarterly basis by FTP burst of data. Reports are due January 31, April 30, July 31, and October 31. Instructions for submitting data using the CDUS can be found on the CTEP website: (<http://ctep.cancer.gov/reporting/cdus.html>).

**Note:** If your study has been assigned to CDUS-Complete reporting, **all** adverse events (both routine and expedited) that have occurred on the study and meet the mandatory CDUS reporting

guidelines must be reported via the monitoring method identified above. If your study has been assigned to CDUS-Abbreviated reporting, no adverse event reporting (routine or expedited) is required to be reported via CDUS, but expedited adverse events are still required to be submitted via CTEP-AERS.

## 10.0 DRUG INFORMATION

### 10.1 General Considerations

Chemotherapy drug dosages need not be changed unless the calculated dose changes by  $\geq 10\%$ .

### 10.2 Fluorouracil (Adrucil®, 5FU)

#### *Procurement*

Commercial supplies. Pharmacies or clinics shall obtain supplies from normal commercial supply chain or wholesaler.

#### *Formulation*

Commercially available for injection 50 mg/mL (10 mL, 20 mL, 50 mL, and 100 mL).

#### *Preparation, Storage and Stability*

Store intact vials at room temperature and protect from light. A slight discoloration may occur with storage but usually does not denote decomposition. Dilute in 50 – 1000 mL of 0.9% NaCl or D5W. If exposed to cold, a precipitate may form; gentle heating to 60°C will dissolve the precipitate without impairing the potency. Solutions in 50 – 1000 mL 0.9% NaCl or D5W or undiluted solutions in syringes are stable for 72 hours at room temperature. Fluorouracil should not be co-administered with either diazepam, doxorubicin, daunorubicin, idarubicin, cisplatin, or cytarabine. However, fluorouracil and leucovorin are compatible for 14 days at room temperature. Fluorouracil is compatible with vincristine, methotrexate, and cyclophosphamide.

#### *Administration*

Fluorouracil may be given IV bolus or IV infusion. Refer to the treatment section for specific administration instructions. Avoid extravasation, may be an irritant.

#### *Drug Interactions*

Fluorouracil may increase effects of warfarin. Avoid ethanol (due to GI irritation). Avoid black cohosh.

#### *Pharmacokinetics*

Distribution:  $V_d \sim 22\%$  of total body water; penetrates extracellular fluid, CSF, and third space fluids (e.g. pleural effusions and ascitic fluid)

Metabolism: Hepatic (90%); via a dehydrogenase enzyme; Fluorouracil must be metabolized to be active.

Half-life Elimination: Biphasic: Initial: 6-20 minutes; two metabolites, FdUMP and FUTP, have prolonged half-lives depending on the type of tissue.

Excretion: Lung (large amounts as  $\text{CO}_2$ ); urine (5% as unchanged drug) in 6 hours.

#### *Adverse Events*

Consult the package insert for the most current and complete information.

Common Known Potential Toxicities, > 10%:

Dermatologic: Dermatitis, pruritic maculopapular rash, alopecia.

Gastrointestinal (route and schedule dependent): Heartburn, nausea, vomiting, anorexia, stomatitis, esophagitis, anorexia, diarrhea. GI toxicity (anorexia, nausea, and vomiting) is generally more severe with continuous-infusion schedules.

Emetic Potential: <1000 mg: Moderately low (10% to 30%) ≥ 1000 mg: Moderate (30% to 60%)

Hematologic: Leukopenia; Myelosuppressive (tends to be more pronounced in patients receiving bolus dosing of FU). Decreased white blood cell count with increased risk of infection; decreased platelet count with increased risk of bleeding.

Local: Irritant chemotherapy.

Less Common Known Potential Toxicities, 1% - 10%:

Dermatologic: Dry skin

Gastrointestinal: GI ulceration

Rare Known Potential Toxicities, <1% (Limited to Important or Life-threatening):

Cardiac enzyme abnormalities, chest pain, coagulopathy, dyspnea, ECG changes similar to ischemic changes, hepatotoxicity; hyperpigmentation of nail beds, face, hands, and veins used in infusion; hypotension, palmar-plantar syndrome (hand-foot syndrome), photosensitization. Cerebellar ataxia, headache, somnolence, ataxia are seen primarily in intracarotid arterial infusions for head and neck tumors.

*Nursing Guidelines*

Monitor complete blood count and platelet count. Instruct patient to report signs and symptoms of infection, unusual bruising or bleeding to the physician.

Administer antiemetics as indicated.

Diarrhea may be dose-limiting; encourage fluids and treat symptomatically.

Assess for stomatitis; oral care measures as indicated. May try vitamin E oil dabbed on sore, six times daily. Cryotherapy recommended with IV push administration.

Monitor for neurologic symptoms (headache, ataxia).

Inform patient of potential alopecia.

Those patients on continuous infusion may need instruction regarding central intravenous catheters and portable intravenous or IA infusion devices.

5FU-induced conjunctivitis is a common problem. Advise patient to report any eye soreness or redness to the healthcare team.

Photosensitivity may occur. Instruct patients to wear sun block when outdoors.

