**8.1.10 Neurologic Toxicity Due to Oxaliplatin**

Patients receiving oxaliplatin on this study should be counseled to avoid cold drinks, chewing of ice chips, and exposure to cold water or air because the neurotoxicity often seen with oxaliplatin appears to be exacerbated by exposure to cold. The period of time during which the patient is at risk for these cold-induced sensory neuropathies is not well documented. Patients should exercise caution regarding cold exposure during the treatment period. Peripheral sensory neuropathies can occur at any time after receiving oxaliplatin therapy.

Supportive care is allowed at the discretion of the treating physician. For pharyngo-laryngeal dysesthesia, it is recommended to increase the duration of oxaliplatin infusion to 6 hours for subsequent cycles.

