### *Administration*

Should be administered IV infusion (2 hours) and is not intended for intrathecal use.

Combination Therapy with Fluorouracil: Fluorouracil is usually given after, or at the midpoint, of the leucovorin infusion. Leucovorin is usually administered by IV infusion. Other administration schedules have been used; refer to individual protocols.

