#### *Nursing Guidelines*

Headache may occur. Advise patient that analgesics such as Tylenol may help. Instruct patient to report any headache that is unrelieved.

Observe for sensitization reaction (rash, hives, pruritus, facial flushing, and wheezing).

May potentiate the toxic effects of fluoropyrimidine (5-FU) therapy, resulting in increased hematologic and gastrointestinal (diarrhea, stomatitis) adverse effects. Monitor closely.

May cause mild nausea or upset stomach. Administer antiemetics if necessary and evaluate for their effectiveness.

**10.4 Oxaliplatin (Eloxatin®, OXAL)***Procurement*

Commercial supplies. Pharmacies or clinics shall obtain supplies from normal commercial supply chain or wholesaler.

*Formulation*

Commercially Available for Injection as: Solution [preservative free]: 5 mg/mL (10 mL, 20 mL, and 40 mL)

*Preparation, Storage and Stability*

Refer to package insert for complete preparation and dispensing instructions. Store intact vials in original outer carton at room temperature and; do not freeze. According to the manufacturer, solutions diluted for infusion are stable up to 6 hours at room temperature or up to 24 hours under refrigeration. Oxaliplatin solution diluted with D5W to a final concentration of 0.7 mg/mL (polyolefin container) has been shown to retain >90% of its original concentration for up to 30 days when stored at room temperature or refrigerated; artificial light did not affect the concentration (Andre, 2007). As this study did not examine sterility, refrigeration would be preferred to limit microbial growth. Do not prepare using a chloride-containing solution (e.g. NaCl). Dilution with D5W (250 or 500 mL) is required prior to administration. Infusion solutions do not require protection from light.

*Administration*

Refer to the treatment section for specific administration instructions. Administer as I.V. infusion over 2 hours. Flush infusion line with D5W prior to administration of any concomitant medication. Patients should receive an antiemetic premedication regimen. Cold temperature may exacerbate acute neuropathy. Avoid mucositis prophylaxis with ice chips during oxaliplatin infusion.

*Drug Interactions*

Increased Effect/Toxicity: Nephrotoxic agents may increase Oxaliplatin toxicity.

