When administered as sequential infusions, observational studies indicate a potential for increased toxicity when platinum derivatives (carboplatin, cisplatin, oxaliplatin) are administered before taxane derivatives (docetaxel, paclitaxel).

Decreased Effect: Oxaliplatin may decrease plasma levels of digoxin

*Pharmacokinetics*

Distribution: Vd: 440 L

Protein Binding: >90% primarily albumin and gamma globulin (irreversible binding to platinum)

Metabolism: Nonenzymatic (rapid and extensive), forms active and inactive derivative phase: 16.8 hours

Excretion: Primarily urine (~54%); feces (~2%)

*Adverse Events*

Consult the package insert for the most current and complete information. Percentages reported with monotherapy.

Common Known Potential Toxicities, > 10%:

Central nervous system: Fatigue, fever, pain, headache, insomnia

Gastrointestinal: Nausea, diarrhea, vomiting, abdominal pain, constipation, anorexia, stomatitis

Hematologic: Anemia, thrombocytopenia, leukopenia

Hepatic: Liver enzymes increased

Neuromuscular & skeletal: Back pain, peripheral neuropathy (may be dose limiting). The most commonly observed oxaliplatin-related toxicity is acute and cumulative neurotoxicity, observed in patients treated at doses above 100 mg/m^2/cycle. This neurotoxicity has included paresthesias and dysesthesias of the hands, feet, and perioral region as well as unusual laryngopharyngeal dysesthesias characterized by a loss of sensation of breathing without any objective evidence of respiratory distress (hypoxia, laryngospasm, or bronchospasm). OXAL neurotoxicity appears to be exacerbated by exposure to cold. Patients on this study will be counseled to avoid cold drinks and exposure to cold water or air. Should a patient develop laryngopharyngeal dysesthesia, their oxygen saturation should be evaluated via a pulse oximeter; if normal, an anxiolytic agent should be given and the patient observed in the clinic until the episode has resolved. Because this syndrome may be associated with the rapidity of OXAL infusion, subsequent doses of OXAL should be administered as a 6-hour infusion (instead of the normal 2-hour infusion).

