Otic: Clinical ototoxicity occurs in less than 1% of patients following oxaliplatin administration, and severe ototoxicity has not been reported.

*Nursing Guidelines*

GI toxicity similar to cisplatin occurs with doses above 30 mg/m^2. It can be almost constant and frequently severe, but not always dose-limiting. Monitor for nausea and vomiting and treat accordingly.

Dose-limiting side effect can be paresthesias of hands, fingers, toes, pharynx, and occasionally cramps which develops with a dose-related frequency (>90 mg/m^2). Duration of symptoms tend to be brief (less than a week) with the first course, but longer with subsequent courses. Phase I patients have reported exacerbation of paresthesias by touching cold surfaces or exposure to cold. Advise patient of these possibilities and instruct patient to report these symptoms to the health care team. Also advise patient to refrain from operating dangerous machinery that requires fine sensory-motor coordination, if symptoms appear.

These sensory neuropathies developed after subsequent courses with increasing intensity (Grade 3 toxicity after the fourth course) and with increasing duration. In 63% of the patients tested in phase I at high doses (135-200 mg/m^2), neuropathies became long-term with slow reversal over several months. Disabling walking and handwriting difficulties, as well as mouth and throat dysesthesias and laryngospasms were seen. Instruct patient to report any swallowing difficulties or gait changes.

OXAL is incompatible with NS. Flush lines with D5W prior to and following OXAL infusion.

Low back pain is a common side effect, perhaps a form of hypersensitivity reaction. Instruct patient in good body mechanics, advise light massage, heat, etc.

Laryngopharyngeal dysesthesia (LPD) occurs in about 15% of patients and is acute, sporadic, and self-limited. It usually occurs within hours of infusion, is induced or exacerbated by

exposure to cold, and presents with dyspnea and dysphagia. The incidence and severity appear to be reduced by prolonging infusion time. Instruct patient to avoid ice and cold drinks the day of infusion.

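### Outside Germany, the fluorouracil nursing guidelines in Section 10.2 recommend cryotherapy with the 5-FU push and make no exception for oxaliplatin, against Sections 8.1.10 and 10.4

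*Combined protocol and SAP*

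**What the plan says.** Section 10.2 (Fluorouracil), Nursing Guidelines: "Cryotherapy recommended with IV push administration". The sentence sits with the advice on checking for stomatitis and caring for mouth sores. It does not define cryotherapy or mention oxaliplatin.

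Section 8.1.10, which deals with nerve damage from oxaliplatin, reads: "Patients receiving oxaliplatin on this study should be counseled to avoid cold drinks, chewing of ice chips, and exposure to cold water or air". It adds, later in the same section: "Patients should exercise caution regarding cold exposure during the treatment period".

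Section 10.4 (Oxaliplatin) addresses cold in three places:

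- Administration: "Avoid mucositis prophylaxis with ice chips during oxaliplatin infusion".
- Adverse Events: "Patients on this study will be counseled to avoid cold drinks and exposure to cold water or air".
- Nursing Guidelines: "Instruct patient to avoid ice and cold drinks the day of infusion".

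Sections 7.1 and 7.2 schedule oxaliplatin, leucovorin and the 5-FU bolus on Day 1 of each 14-day cycle, with fluorouracil listed last. Leucovorin may run concurrently with oxaliplatin. For Germany, Section 2.3 of the AIO group-specific appendix takes precedence over Section 10.2.

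**The concern.** Someone working from the fluorouracil pages is advised to offer cooling with the push. Someone working from the oxaliplatin text is told to keep the same patient away from ice on the same day.

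The protocol gives its own reasons for avoiding cold. Sections 8.1.10 and 10.4 link cold to worse oxaliplatin neurotoxicity. The nursing guidelines in Section 10.4 put laryngopharyngeal dysesthesia at about 15% of patients and say that cold can bring it on or worsen it. An episode has consequences: Section 10.4 calls for an oximetry check, an anxiolytic if saturation is normal, and observation in clinic. Section 8.2.1.4 then lengthens oxaliplatin to 6 hours in every later cycle.

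What is at stake is a patient's exposure to a trigger that the protocol itself warns against. The trial's inference is not at stake.

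**Working it through.** No figure in the plan needs reproducing. The check sets the instructions side by side and asks whether meaning, timing or precedence reconciles them.

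1. **Meaning.** Cryotherapy is undefined in Section 10.2. Its place beside the stomatitis advice points to oral ice, and Section 10.4 Administration names ice chips as mucositis prophylaxis. This is an inference, but the most natural one.

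2. **Timing.** The instructions differ in how long they apply.

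| Instruction | Period covered | Covers a push after oxaliplatin ends? | Covers a push during oxaliplatin? |
|---|---|---|---|
| 8.1.10 | No time limit on the ice-chip advice; caution about cold throughout treatment | Yes | Yes |
| 10.4 Nursing Guidelines | Whole day of infusion | Yes | Yes |
| 10.4 Administration | Oxaliplatin infusion only | No | Yes |

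   In the listed order the push follows oxaliplatin, so the Administration sentence alone would not conflict. The push could fall during oxaliplatin if leucovorin runs concurrently, because Section 10.3 says "Fluorouracil is usually given after, or at the midpoint, of the leucovorin infusion". In either case Section 8.1.10 and the 10.4 nursing guideline apply, so timing does not remove the conflict.

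3. **Precedence.** Under Administration, Section 10.2 says "Refer to the treatment section for specific administration instructions". That deferral concerns administration only, and Sections 7.0 to 7.2 are silent on ice and cold. No text ranks Section 8.1.10 or 10.4 above Section 10.2. The one precedence rule, in Section 2.3 of the AIO appendix, covers Germany.

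4. **Scope.** The conflict arises in cycles that include both oxaliplatin and the bolus. Sections 7.1 and 7.2 give 12 cycles of mFOLFOX6, so the maximum is 12 Day 1 visits per patient. If Cycle 1 came before registration, it is 12 − 1 = 11. The count falls if the bolus is dropped (Section 8.2.1.1) or oxaliplatin is omitted (Sections 8.2 and 8.2.1.4).

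5. **Size of harm.** This cannot be computed. The documents give no excess rate of neurotoxicity from oral cooling. The 15% figure is the overall frequency of laryngopharyngeal dysesthesia, not an increment due to ice.

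**The case against.** The strongest reply is that the study-specific text already settles the matter. Section 8.1.10 and three places in Section 10.4 point the same way, some of them addressed expressly to patients on this study. The line in Section 10.2 belongs to visibly generic drug information, which also mentions intracarotid infusions for head and neck tumors. Both sides of the clash are advisory, Section 8.1.10 leaves supportive care to the treating physician, and Section 5.0 expects physicians experienced with such treatment. Nothing shows that any patient was given ice because of Section 10.2.

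Exposure may also be over. This version carries text effective August 30, 2024. The one end-of-treatment date given, for Germany, is February 2023, and the listed changes mostly concern follow-up and data submission.

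Part of this stands. Experienced staff would probably follow the oxaliplatin text, no harm is shown, and if nobody remains on mFOLFOX6 the edit only corrects the wording. But Section 10 is part of the operative protocol. Relying on staff to disregard a stated recommendation is not a safeguard, and the documents do not settle who outside Germany is still on treatment.

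**Conclusion.** The concern holds. Outside Germany, Section 10.2 recommends something that Section 8.1.10 and the nursing guidelines in Section 10.4 tell patients on oxaliplatin to avoid, in every cycle that gives both oxaliplatin and the 5-FU bolus. The conclusion assumes that cryotherapy means oral ice; if the sponsor meant something else, the sentence still needs clarifying.

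This is a minor consistency correction on a patient-safety point, with no harm quantified. It affects both arms alike, and no effect on DFS, power or alpha is expected.

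**What to change.** In the Section 10.2 nursing guidelines, delete the cryotherapy sentence, or replace it with: *Do not use oral cryotherapy in patients receiving oxaliplatin (see Section 8.1.10).*

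Do not add wording that allows ice whenever oxaliplatin is omitted. Section 8.2.1.4 stops oxaliplatin for persistent grade 3 or any grade 4 neurotoxicity, and those patients should not be steered towards cold. Section 8.1.10 also asks for caution throughout the treatment period.

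Optionally, widen the ice-chip bar in Section 10.4 Administration from the infusion itself to the whole day of infusion, so that it matches the nursing guidelines in the same section.

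The cost is one sentence, plus one optional phrase, at the next amendment. Scheduled procedures, data collection and analysis do not change.
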